Upon completion of the maintenance period (Week 52), all patients will have the option to enter the 3-year long-term extension Study I6T-MC-AMAZ (AMAZ) or enter the post-treatment follow-up period (12 weeks following SC administration). With sponsor approval, additional dosing at Week 52 and unscheduled visits (UV) beyond Week 52 may occur as needed for patients eligible to enroll in Study AMAZ where the clinical trial site is not yet open. Patients must have completed all procedures at Visit 16 and additional dosing should occur at 4-week intervals (±7 days) from the prior dose. Patients who discontinue while receiving IV dosing will undergo procedures for early termination of the study drug, including post-treatment follow-up for 16 weeks as described in the Schedule of Activities (Section 2).

Figure AMBU.1 illustrates the study design

Study governance considerations are described in detail in Appendix 3.

[figure not shown]

Figure AMBU.1. Illustration of study design for clinical protocol I6T-MC-AMBU.

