6.1. Inclusion Criteria

Patients are eligible to be included in the study only if they meet all of the following criteria within the screening period, which is CCI [REDACTED], unless otherwise specified below:

Informed Consent

- [1] Have given assent (if appropriate) with parent/legal guardian signed informed consent approved by the ethical review board (ERB) governing the site.

Patient Characteristics

[figure not shown]
- [2] Male or female patients weighing >10 kg AND ≥ 2 and <18 years of age at the time of informed consent.

[2a]

CCI [REDACTED]

[2b]

CCI [REDACTED]

[3] Both the parent or legal representative and child (if capable) must agree to comply with the requirements of the protocol.

[4] CCI [Redacted]

Type of Patient and Disease Characteristics

[5] Have an established diagnosis of UC of ≥ 3 months in duration before baseline, CCI [Redacted]

[6] Have moderately to severely active UC as defined by a CCI [Redacted] within CCI [Redacted] before first dose of study treatment (baseline).

[7] Have evidence of UC extending proximal to the rectum CCI [Redacted]

Prior Medication Failure Criteria

[8] Patients must have an inadequate response to, loss of response to, or intolerance to at least 1 of the medications described in Criteria [8a] OR [8b]. **Documentation of dose, frequency, route of administration, and duration of the prior failed treatment is required.**

[8a] **Biologic-naive patients:** Patients who have an inadequate response to, loss of response to, or are intolerant to at least 1 of the following medications:

- Corticosteroids
 - Corticosteroid-refractory colitis, defined as signs and/or symptoms of active UC despite a CCI [REDACTED]

CCI [REDACTED]

CCI [REDACTED]

- Immunomodulators:
 - Signs and/or symptoms of persistently active disease despite at least 3 months' treatment with 1 of the following:

- Oral AZA CCI [REDACTED] or 6-MP CCI [REDACTED], or

CCI [REDACTED]

- History of intolerance to at least 1 immunomodulator CCI [REDACTED]

Discontinuation despite clinical benefit does not qualify as having failed or being intolerant to UC non-biologic therapy.

[8b] **Biologic/JAK inhibitor-experienced patients:** Patients who have an inadequate response to, CCI [REDACTED] to biologic therapy for UC (such as anti-TNF antibodies or anti CCI [REDACTED] antibodies) and/or to JAK inhibitors (such as tofacitinib), as described below.

Investigators must document an adequate trial of the medication.

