9.1.6. Growth and Pubertal Assessments

9.1.6.1. Occipital Head Circumference

Occipital head circumference measurements will be performed on patients less than 3 years of age at baseline. Measurements will be taken at baseline and then approximately Q12W thereafter, until the patient reaches the age of 3 years.

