		response	reduction in baseline PUCAI score of ≥20	missing.
		1	points.	8

Measure	Description	Variable	Derivation / Comment	Definition of Missing
	CCI			
Histo-Endo	Combined histology and endoscopic endpoints.	Histologic-endoscopic mucosal improvement Histologic-endoscopic	Histologic improvement and endoscopic remission. Defined as achieving both histologic	Missing if any component of the definition is missing. Missing if any component of the
		mucosal remission	remission and endoscopic remission	definition is missing.
CRP	C-reactive protein (CRP) is a biomarker of inflammation.	CRP	Lab value. May be transformed if needed.	Single lab value. Missing if missing.
Fecal calprotectin	Fecal calprotectin is used as a biomarker of intestinal inflammation in clinical practice.	Fecal calprotectin	Lab value. May be transformed if needed.	Single lab value. Missing if missing.
Growth and Pubertal Assessments	Occipital head circumference	Head circumference	Occipital head circumference measurements will be performed on patients less than 3 years of age at baseline. Measurements will be taken at baseline and then approximately Q12W thereafter, until the patient reaches the age of 3 years.	Data will be missing for patients who are 3 years or older at entry. Missing if missing.
	Change from baseline in height (cm)	Height CFB	Change from baseline in height (cm) at all study visits. Height is measured 3 times at all visits, height at each visit is calculated	Missing if baseline height or height at visit is missing.

Measure	Description	Variable	Derivation / Comment	Definition of Missing
			using the average of the 3 measurements.	
	Change from baseline in weight (kg)	Weight CFB	Change from baseline in weight (kg) at all study visits.	Missing if baseline weight or weight at visit is missing.
	Height Z-score and percentile by sex and age will be calculated using the CDC growth data shown at: https://www.cdc.gov/nccdphp/dnpao/growthcharts/resources/sas.htm	Height Z-score Height Percentile	Observed height z-score and percentile by sex and age	Missing if height at visit is missing.
	This approach uses a Box-Cox transformation to calculate the height z-score and percentile of the normal distribution for the corresponding age and sex.			
	Height Percentile Change from Baseline	Height Percentile CFB	Change from Baseline is calculated as Present height percentile – Baseline height percentile	Missing if baseline height or height at visit is missing.

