	PUCAI clinical response	Proportion for each weight/treatment	mITT	Weeks 12 and 52
		dose group along with the 95%	mITT who achieve PUCAI	Week 52
		2-sided CI with NRI and as observed.	clinical response at Week 12	
	PUCAI CFB	Descriptive statistics and 95% CI for	mITT	Weeks 12, 24, 36, and 52
		mean with mBOCF and as observed.		

		Analysis Method	Population	
Measure	Variable	(Section 6.1.3)	(Section 6.1.1)	Time Point(s)
Height	Height Velocity	Descriptive statistics and 95% CI for	mITT, by gender and age	Weeks 12, 24, and 52
	II : 14 CED	mean.	group	W 1 12 24 152
	Height CFB	Descriptive statistics and 95% CI for mean.	mITT	Weeks 12, 24, and 52
	Height Percentiles CFB	Descriptive statistics and 95% CI for mean.	mITT	Weeks 12, 24, and 52
Weight	Weight CFB	Descriptive statistics and 95% CI for mean.	mITT	At each scheduled visit.
	Weight Percentiles CFB	Descriptive statistics and 95% CI for mean.	mITT	Weeks 12, 24, and 52
Occipital head circumference	Head circumference	Descriptive statistics and 95% CI for mean.	mITT only on those patients less than 3 years at baseline	At all applicable visits (Week 12 + Q12W)
Puberty Development	Testosterone CFB	Descriptive statistics and 95% CI for mean.	mITT – males who are 9 years or older	Weeks 12, 36, and 52
	Estradiol CFB	Descriptive statistics and 95% CI for mean.	mITT – females who are 9 years or older without the date of onset of menstruation.	Weeks 12, 36, and 52
Abdominal Pain NRS	Abdominal Pain NRS score CFB	Descriptive statistics and 95% CI for mean with mBOCF and as observed.	mITT, summarized by age group	Weeks 12 and 52
. The	CCI			Week 12 and 52
CCI			mITT	Weeks 12 and 52
Histopathology	Histologic Remission	Proportion for each weight/treatment dose group along with the 95% 2-sided CI with NRI and as observed.	mITT	Weeks 12 and 52
	Histologic Improvement	Proportion for each weight/treatment dose group along with the 95% 2-sided CI with NRI and as observed.	mITT	Weeks 12 and 52

		Analysis Method	Population	
Measure	Variable	(Section 6.1.3)	(Section 6.1.1)	Time Point(s)
	Histologic-Endoscopic	Proportion for each weight/treatment	mITT	Weeks 12 and 52
	Mucosal Improvement	dose group along with the 95%		
		2-sided CI with NRI and as observed.		
	Histologic-Endoscopic	Proportion for each weight/treatment	mITT	Weeks 12 and 52
	Mucosal Remission	dose group along with the 95%		
		2-sided CI with NRI and as observed.		

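### Head circumference is averaged raw by visit although measurement stops at age 3, so each later mean covers a younger group and tends to understate growth

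*Protocol*

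**What the plan says.** - **Entry.** Protocol section 6.1 admits children "≥ 2 and <18 years of age at the time of informed consent".
- **Who is measured.** Protocol section 9.1.6.1: "Occipital head circumference measurements will be performed on patients less than 3 years of age at baseline".
- **When it stops.** The same section: "Measurements will be taken at baseline and then approximately Q12W thereafter, until the patient reaches the age of 3 years". SAP Table AMBU.6.4 repeats the rule, ending measurement when the child "reaches the age of 3 years".
- **Scheduled visits.** The protocol's Schedule of Activities marks head circumference at Visits 2, 6, 9, 12 and 16. SAP Appendix 1 gives Visit 6 as Week 12 and Visit 16 as Week 52. With four-weekly visits between them, Visits 9 and 12 are Weeks 24 and 36.
- **Analysis.** In SAP Table AMBU.6.5 the variable is head circumference itself. The method is "Descriptive statistics and 95% CI for mean", the population is "mITT only on those patients less than 3 years at baseline", and the time-point cell begins "At all applicable visits (Week 12 + Q12W". No change from baseline, percentile, z-score or imputation is named in that row.
- **Neighbouring rows.** Height and weight each have a change-from-baseline row and a percentile-change row. SAP Table AMBU.6.4 also defines z-scores by sex and age for both.
- **Missing data.** SAP Table AMBU.6.4 treats head circumference as missing for children aged 3 or over at entry. It says nothing about children who turn 3 during the study.

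**The concern.** Departure from this summary depends on age, and head size rises with age. The children who stop being measured are always the oldest, so those who remain are younger than the group that supplied the baseline mean. A series of raw visit means then mixes two things: growth of the children still measured, which raises the mean, and loss of the oldest, which lowers it. Read as a growth trend, it tends to be too flat. In a paediatric growth measure, someone could take that for slowed head growth on treatment when it comes from the measurement rule.

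The age limit itself is not the problem. The gap is in the SAP row, which does not allow for the limit.

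**Working it through.** The documents give no coverage or growth figure for head circumference, so there is nothing to reproduce.

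**Set-up.** Let baseline age be 2 + x years, with x from 0 to 1. A child is measured at time t if x + t < 1, where t = 7 × week / 365.25. Data are taken as observed, since the row names no imputation. The age distribution and growth curve below are assumptions.

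**Uniform ages, linear growth.** Coverage is 1 − t. Children still measured have mean age 2.5 + t/2 at the visit, against 2.5 + t for the whole group.

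| Week | t (years) | Still measured | Rise in mean age, those measured | Rise, whole group |
|---|---|---|---|---|
| 12 | 0.230 | 77% | 0.115 | 0.230 |
| 24 | 0.460 | 54% | 0.230 | 0.460 |
| 36 | 0.690 | 31% | 0.345 | 0.690 |
| 48 | 0.920 | 8% | – | – |
| 52 | 0.997 | 0.3% | – | – |

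The trend in raw means shows (t/2)/t = 0.50 of true growth.

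**Other assumptions.** Apparent growth divided by true growth:

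| Entry ages; growth | Week 12 | Week 24 | Week 36 |
|---|---|---|---|
| Uniform; growth rate halves between ages 2 and 3 | 0.57 | 0.60 | 0.62 |
| Skewed towards 3, Beta(2,1); linear | 0.33 | 0.33 | 0.33 |
| Strongly skewed towards 3, Beta(4,1); linear | 0.20 | 0.20 | 0.20 |
| Skewed towards 2, Beta(1,2); linear | 0.88 | 0.79 | 0.73 |
| Centred, Beta(2,2); linear | 0.76 | 0.64 | 0.57 |

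For the first row, take H(x) = x − x²/4, whose slope falls from 1 to 0.5. The ratio is then (5 − t)/(9 − 3t); at Week 12, 4.77/8.31 = 0.57.

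**Small groups.** With uniform ages and linear growth, and given that someone is still measured at Weeks 12 to 36, the average ratio is 1.00 for one child, 0.59 to 0.70 for two, and 0.50 to 0.54 for five.

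**How many children.** The documents do not say. If 30 patients were spread evenly over ages 2 to <18, 30/16 = 1.9 would be under 3, and P(none) = (15/16)^30 = 0.14. If the 20 patients of ≤40 kg were spread evenly over ages 2 to <12, 20/10 = 2.0 would be, and P(none) = 0.9^20 = 0.12. P(at least 3) is 0.29 to 0.32 and P(at least 5) about 0.04.

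**Week 52.** This is day 364, and entry is at 2 years or older at consent. An on-time visit has coverage of 0% to 0.7% under every age distribution tried. With uniform ages it is 2.3% if the visit is 7 days early (1 − 357/365.25), and 0% if baseline falls 28 days after consent.

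**Within-child change instead.** Under linear growth its ratio to whole-group growth is 1.00 at every visit. With H as above and uniform ages, mean change among those still measured is 0.75t, against t(0.75 − 0.25t) for the whole group. The ratios are 0.75/0.6925 = 1.08, 0.75/0.635 = 1.18 and 0.75/0.5775 = 1.30 at Weeks 12, 24 and 36. The remaining children are younger and grow faster.

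**The case against.** The strongest reply is that little depends on this row.

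- Head circumference is not in the visible entries of Protocol Table AMBU.2 or SAP Table AMBU.4.2. The study is uncontrolled and plans no treatment comparisons, and growth is also followed through height and weight.
- With 0 to 3 children split between two dose groups of ≤40 kg, a cell may hold one child or none, leaving hardly a trend to misread.
- SAP section 6.1.3 requires n at each visit, so the shrinking group will be visible. It also allows mean change from baseline where appropriate.
- The row is limited to applicable visits, which can be read as visits at which the child is still measured.

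The first two points stand and keep the matter minor. The third stands in part: n reveals that children have left but not that they were the oldest, and a discretionary change summary is weaker than the named rows given to height and weight. The fourth does not help, because a mean over children still measured is exactly the shifting group described.

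A reader might go further and infer that the trend will show half of true growth. The documents do not support that. It needs uniform ages and linear growth, neither of which they state.

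A reader might also infer that the SAP plans a Week 52 mean that is empty. The schedule marks Visit 16, but the SAP row gives 12-weekly applicable visits and names no Week 52 summary, and the age limit already removes almost everyone. That deserves a note only.

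**Conclusion.** The point holds as a minor flaw in one descriptive SAP row. Two things follow from the documents alone: the oldest children leave first, and almost none can still be under 3 at Week 52. Given that heads grow between ages 2 and 3, raw visit means tend to understate growth whenever more than one child contributes and some turn 3.

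The amount is not determined. The trend shows about 0.2 to 0.9 of true growth over the age and growth assumptions tried, 0.5 under uniform ages with linear growth, and all of it with a single child. No endpoint test or dose decision depends on the result.

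**What to change.** In the head circumference row of SAP Table AMBU.6.5:

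1. Replace the raw mean with within-child change from baseline among children measured at both visits, at Weeks 12, 24 and 36. Alternatively use an age- and sex-standardised value, as the SAP does for height and weight, naming the reference.
2. Show n and age at each visit, because simple change among the younger children who remain can overstate whole-group growth (about 8% to 30% at Weeks 12 to 36 if growth slows by half between ages 2 and 3).
3. Add a by-patient listing. With one child in a dose group no confidence interval for a mean can be calculated, and the listing is the informative display.
4. State in SAP Table AMBU.6.4 that children who turn 3 are no longer measured by design, and that no Week 52 mean is expected.

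The cost is one table row, a sentence in the definitions and a short listing. No new measurement is needed, and the protocol's measurement rule stays as it is.

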9.1.6.2. Height Velocity

Height will be collected 3 times per visit at the visits indicated in Section 2 using a stadiometer or other instrument of equivalent measuring capacity. Observed height velocity by gender and age group will be calculated at CCI [REDACTED], based on height measurements from the 3 to 12 months (preferably 4 to 6 months) preceding the study (from screening) or those obtained at baseline according to the following formula:

- $(\text{Present Height [cm]} - \text{Previous Height [cm]}) / \text{Interval (months) Between Measurements} \times 12$

Age-specific z-scores for height velocity by gender and age group will be calculated for each patient with reference to standard height velocity tables according to the following formula:

- $(\text{Observed Height Velocity [cm/y]} - \text{Mean Height Velocity for Age and Sex [cm/y]}) / (\text{Standard Deviation of the Mean})$

Full details on height velocity analyses can be found in the SAP.

9.1.6.3. Assessment of Puberty

CCI [REDACTED]

The date of onset of menstruation will also be collected.

9.1.7. Health Outcomes Instruments

Observer-reported outcomes will be used in place of patient-reported outcomes for children less than CCI [REDACTED] for the following scales. The patient's age at entry into the study will determine which scale/instrument is used and this will not change as the patient ages during the study.

Abdominal Pain Numeric Rating Scale: The abdominal pain numeric rating scale (NRS) is a single item that measures the “worst abdominal pain in the past 24 hours” using a Pain NRS ranging from 0 to 5 (8-11 years old) and 0 to 10 (12-17 years old). For children less than 8 years old, caregivers will complete an observer-reported outcome ranging from 0 to 10. Patients or caregivers will be provided with an electronic diary tool during screening to record information daily pertaining to the patient's worst abdominal pain experience.

Urgency Numeric Rating Scale: CCI [REDACTED]

9.1.8. Histopathology Scoring Instrument

The histopathology instruments that will be used for the evaluation of microscopic inflammation and histopathologic disease activity will be specified in the histopathology charter.

9.1.9. Exploratory Assessments

Exploratory endpoints are found in [Table AMBU.2](#). Additional details are provided below.

9.1.9.1. Inflammatory Biomarkers

Fecal calprotectin: Fecal calprotectin is a complex consisting of the calcium-binding proteins S100A8 and S100A9. It is expressed by activated neutrophils (and to a lesser extent by macrophages and monocytes), and fecal levels correlate with the number of neutrophils in the gut (Sands 2015). It is used as a biomarker of intestinal inflammation in clinical practice. Fecal calprotectin will be obtained at time points described in the Schedule of Activities (Section 2).

C-reactive protein (CRP): C-reactive protein is an acute phase protein expressed by hepatocytes in response to inflammatory cytokines, particularly IL-6, TNF, and IL-1 β (Sands 2015). C-reactive protein will be obtained at the time points described in the Schedule of Activities (Section 2).

9.1.9.2. Patient-Reported Outcome/Observer-Reported Outcome Instruments for Exploratory Assessments

Observer-reported outcomes will be used in place of patient-reported outcomes for children less than **CCI** of age.

CCI

9.1.9.3. Extraintestinal Manifestations

Review of extraintestinal manifestations (EIMs) will be performed at the time points described in the Schedule of Activities (Section 2). Extraintestinal manifestations that occur prior to baseline or existing EIMs that change in severity or resolve during the study will be documented on the appropriate eCRF. Extraintestinal manifestations include, but are not limited to: CCI

9.1.9.4. Physician-Reported Instrument

CCI

9.1.10. Appropriateness of Assessments

All of the clinical and safety assessments in this study are standard, widely used, and generally recognized as reliable, accurate, and relevant. The disease activity measurements are used in clinical practice and UC clinical trials, and the health outcomes measures will allow assessment of symptoms and quality of life that are important to patients and their caregivers.

Immunogenicity monitoring will provide information for future development of mirikizumab.

9.2. Adverse Events

Investigators are responsible for monitoring the safety of patients who have entered this study and for alerting Lilly or its designee to any event that seems unusual, even if this event may be considered an unanticipated benefit to the patient.

The investigator is responsible for the appropriate medical care of patients during the study.

Investigators must document their review of each laboratory safety report.

The investigator remains responsible for following, through an appropriate health care option, AEs that are serious or otherwise medically important, considered related to the investigational product or the study, or that caused the patient to discontinue the investigational product before completing the study. The patient should be followed until the event resolves, stabilizes with appropriate diagnostic evaluation, or is reasonably explained. The frequency of follow-up evaluations of the AE is left to the discretion of the investigator. The investigator will record all relevant AE/SAE information in the eCRF.

Lack of drug effect is not an AE in clinical studies, because the purpose of the clinical study is to establish treatment effect.

After the ICF is signed, study site personnel will record via eCRF the occurrence and nature of each patient's preexisting conditions, including clinically significant signs and symptoms of the

disease under treatment in the study. In addition, site personnel will record any change in the condition(s) and any new conditions as AEs. Investigators should record their assessment of the potential relatedness of each AE to protocol procedure or investigational product, via eCRF.

The investigator will interpret and document whether or not an AE has a reasonable possibility of being related to study drug, study device, or a study procedure, taking into account the disease, concomitant treatment, or pathologies.

A “reasonable possibility” means that there is a cause and effect relationship between the investigational product, study device and/or study procedure and the AE. The investigator answers yes/no when making this assessment.

Planned surgeries and nonsurgical interventions should not be reported as AEs unless the underlying medical condition has worsened during the course of the study.

If a patient’s investigational product is discontinued as a result of an AE, study site personnel must report this to Lilly or its designee via eCRF, clarifying if possible, the circumstances leading to any dosage modifications, or discontinuations of treatment.

Care will be taken not to introduce bias when detecting AEs or SAEs. Open-ended and nonleading verbal questioning of the participant is the preferred method to inquire about AE occurrences.

Cardiovascular and venous thromboembolic AEs and other events leading to death are collected as described in Section 9.2.1 and its subsections; also see Section 9.2.2.4.

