9.2.1. Serious Adverse Events

An SAE is any AE from this study that results in one of the following outcomes:

- Death
- Initial or prolonged inpatient hospitalization
- A life-threatening experience (that is, immediate risk of dying)
- Persistent or significant disability/incapacity
- Congenital anomaly/birth defect
- Important medical events that may not be immediately life-threatening or result in death or hospitalization but may jeopardize the patient or may require intervention to prevent one of the other outcomes listed in the definition above. Examples of such medical events include allergic bronchospasm requiring intensive treatment in an emergency room or at home, blood dyscrasias or convulsions that do not result in inpatient hospitalization, or the development of drug dependency or drug abuse.

All AEs occurring after signing the ICF are recorded in the eCRF, assessed for serious criteria, and all serious criteria that are met are recorded in the eCRF. The required timeframe for SAE reporting to the sponsor begins after the patient has signed the ICF and has received

investigational product. However, if an SAE occurs after signing the ICF, but prior to receiving investigational product, the SAE should be reported to the sponsor as per SAE reporting requirements and timelines (see Section 9.2) if it is considered reasonably possibly related to study procedure.

Study site personnel must alert Lilly or its designee of any SAE within 24 hours of investigator's awareness of the event via a sponsor-approved method. If alerts are issued via telephone, they are to be immediately followed with official notification on study-specific SAE forms. This 24-hour notification requirement refers to the initial SAE information and all follow-up SAE information. Patients with a CCI [REDACTED] should have additional data collected using the hepatic eCRF.

Pregnancy (during maternal or paternal exposure to investigational product) does not meet the definition of an AE. However, to fulfill regulatory requirements, any pregnancy that begins at any point after the start of study drug and until at least CCI [REDACTED] after the participant's last dose of study drug should be reported following the SAE process to collect data on the outcome for both mother and fetus.

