Investigators are not obligated to actively seek AEs or SAEs in subjects once they have discontinued and/or completed the study (that is, the patient disposition case report form has been completed). However, if the investigator learns of any SAE, including a death, at any time after a subject has been discharged from the study, and he/she considers the event reasonably possibly related to the study drug or study participation, the investigator must promptly notify Lilly.

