9.2.1.1. Suspected Unexpected Serious Adverse Reactions

Suspected unexpected serious adverse reactions (SUSARs) are serious events that are not listed in the IB and that the investigator identifies as related to investigational product or procedure. United States 21 CFR 312.32 and European Union Clinical Trial Directive 2001/20/EC and the associated detailed guidances or national regulatory requirements in participating countries require the reporting of SUSARs. Lilly has procedures that will be followed for the identification, recording, and expedited reporting of SUSARs that are consistent with global regulations and the associated detailed guidances.

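### Protocol Section 9.2 defines a reasonable possibility of relatedness as an actual cause and effect relationship; read literally, this removes the duty to notify some SAEs learned of after a patient has left the study

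*Protocol*

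**What the plan says.** Protocol Section 9.2 tells investigators to record the potential relatedness of each AE. It then asks them to interpret and document "whether or not an AE has a reasonable possibility of being related to study drug, study device, or a study procedure". The next paragraph defines the key term: a reasonable possibility "means that there is a cause and effect relationship between the investigational product, study device and/or study procedure and the AE". The scale is binary: "The investigator answers yes/no when making this assessment".

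Three later rules use a relatedness judgement:

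- **SAEs learned of after study exit (Section 9.2.1).** Investigators need not actively seek events once a patient has discontinued or completed the study. If one learns of an SAE after discharge and "he/she considers the event reasonably possibly related to the study drug or study participation, the investigator must promptly notify Lilly".
- **SUSARs (Section 9.2.1.1).** These are "serious events that are not listed in the IB and that the investigator identifies as related to investigational product or procedure".
- **SAEs between consent and first dose (Section 9.2.1).** These are reported on SAE timelines "if it is considered reasonably possibly related to study procedure".

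**The concern.** The question asks about a possibility, while the definition requires that the causal link exists. The definition has no *may* or *suggests*, and a yes/no answer leaves nowhere to put an event that is possible but not established. An investigator who follows the definition must answer no for such an event.

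This matters here because the study is open-label, has no control group, enrols about 30 children and allows background immunomodulators and corticosteroids (Protocol Sections 5.2 and 5.4). Cause can seldom be established for a single event in that setting, so many judgements will sit between possible and established. At stake is whether the reporting rules that depend on the answer work as intended, and whether sites answer the question in the same way.

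**Working it through.** No arithmetic applies. The check follows the definition to each rule that uses it, and then to the SAP.

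**Step 1: the definition against its own section.** Section 9.2 contains three statements of the standard: potential relatedness, reasonable possibility, and the existence of a causal link. The first two agree and the third is stricter. Nothing is redacted in these sentences, and no other section softens the definition.

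**Step 2: direction.** Every event with an established causal link also has a reasonable possibility of one, but the reverse is not true. Relative to the question, the definition can therefore only turn yes answers into no answers.

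**Step 3: each dependent rule, for an event that is possibly but not demonstrably related.**

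| Rule | Result if the definition is applied literally | What still catches the event |
|---|---|---|
| SAE learned of after study exit (9.2.1) | The duty to notify is not triggered | No causality-free SAE rule applies at this stage; only the general request in 9.2 to alert the sponsor to anything unusual, which rests on a different judgement |
| Unlisted SAE on study, after dosing (9.2.1.1) | Does not meet the protocol's SUSAR definition, which names only the investigator's judgement | The 24-hour alert for any SAE (9.2.1), and the sponsor's own SUSAR identification procedures (9.2.1.1) |
| SAE before first dose, possibly due to a procedure (9.2.1) | Not reported on SAE timelines | Recording in the eCRF, with the serious criteria met (9.2.1) |

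The pre-dose row is not empty in practice. A screening endoscopy is required (Section 9.1.2), and Section 3.3 names sedation or anesthesia reactions and perforation as procedural risks.

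**Step 4: how wide the post-study gap is.** Section 5.1 provides post-treatment follow-up of 12 weeks after SC administration, or 16 weeks for patients who discontinue during IV dosing. The Schedule of Activities has AE review at Visits 801 and 802. SAEs in that period are still on study and fall under the 24-hour rule. The gap starts only when study participation has ended, and it concerns events that the investigator happens to hear of. For patients who enter the extension study, that study's own rules presumably take over; they are not in these documents.

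**Step 5: the SAP.** The AE, SAE and AE-discontinuation summaries in SAP Sections 6.13.2 and 6.13.3, and the registry summaries in Section 6.18, count patients or events without a relatedness restriction. AESIs are identified by MedDRA queries, term lists or laboratory changes (Section 6.13.7). No listed table changes with the relatedness answer.

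**The case against.** The strongest reply is that one sentence is out of step with its neighbours and that investigators will follow the neighbours. The question itself, the reference to potential relatedness and both triggers in Section 9.2.1 keep the lower bar. Those triggers also use an adverbial form of the term, so it is natural but not explicit that the definition governs them. This stands as a limit on the inference: how investigators would answer is read from the wording, not observed. It does not rescue the sentence. If sites ignore the definition it serves no purpose, if they apply it fewer events are called related, and if they differ the causality data are inconsistent.

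The second reply is that safeguards cover most of the ground. It is largely right. Once dosing has started, an on-study SAE reaches the sponsor within 24 hours with no causality condition. Sponsor procedures cover identifying SUSARs as well as reporting them, and are stated to be consistent with global regulations. Liver abnormalities have their own laboratory-triggered monitoring and eCRF collection (Section 9.4.6.1). These safeguards do not reach the post-study rule.

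A reader might infer that most possible reactions will be answered no and that expedited reporting will be incomplete. The documents do not support either as a fact. The first depends on unknown investigator behaviour. The second overlooks the 24-hour rule and the sponsor's own procedures; the most that can be said is that SUSAR identification could be affected, because the protocol's definition names only the investigator's judgement. Nor does the wording lose pre-dose SAEs from the sponsor's data, since they are in the eCRF.

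**Conclusion.** The definition in Section 9.2 conflicts with the question it defines and should be corrected. The firmest consequence is for SAEs learned of after study exit, where the duty to notify rests on the investigator's relatedness judgement. The effect on SUSARs is a risk that the sponsor's procedures may remove. For pre-dose SAEs, only the reporting timeline is exposed.

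The direction is one-sided, towards fewer events called related, but the size cannot be estimated from the documents. One missed event among about 30 patients would be 1/30, or about 3%, but that is arithmetic on a hypothetical event and says nothing about how often reporting would fail.

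The conclusion assumes that at least some investigators apply the definition as written, and that they read the wording of Section 9.2.1 in its light. No endpoint, sample size or planned analysis is affected.

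**What to change.** Reword the definition in Section 9.2 so that a reasonable possibility means that there are facts or reasons to suggest that a cause and effect relationship *may* exist between the AE and the investigational product, study device or study procedure. Keep the yes/no answer. In Section 9.2.1.1, tie the investigator's identification of an event as related to this same term. Section 9.2.1 already uses the reasonably-possible wording and needs no change.

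The cost is one reworded definition, one aligned phrase and a short note in site training. The downside is that somewhat more events will be called related and reported.
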